ABQoL=Autoimmune Bullous Disease Quality of Life questionnaire; AE=adverse event; BP=bullous pemphigoid; BPDAl=Bullous Pemphigoid Disease Area Index; CR=complete remission; DLQI=Dermatology Life Quality Index; ECG=electrocardiogram; eCRF=electronic case report form; EDV=early discontinuation visit; EFG=efgartigimod PH20 SC; efgartigimod PH20 SC=efgartigimod for SC administration coformulated with rHuPH20; EoTP=end-of-treatment period (visit); F1/F2=follow-up visits 1 and 2; GTI=Glucocorticoid Toxicity Index; GTI-AIS=GTI Aggregate Improvement Score; GTI-CWS=GTI Cumulative Worsening Score; GTI-SL=GTI Specific List; IGA-BP=Investigator Global Assessment of Bullous Pemphigoid; NA=not applicable; NRS=numerical rating scale; OCS=oral corticosteroids; PBMC=peripheral blood mononuclear cell; PD=pharmacodynamics; PK=pharmacokinetics; PR=partial remission; QoL=quality of life; rHuPH20=recombinant human hyaluronidase PH20; SC=subcutaneous; SoA=schedule of activities; UNS=unscheduled visit; W=week

Note: Assessments indicated in gray font will only be recorded on the ARGX-113-2009 eCRF and not on the ARGX-113-2010 eCRF.

^a The baseline visit will occur on the same day as the EoTP visit of ARGX-113-2009. All baseline assessments will be performed before administration of efgartigimod PH20 SC. Assessments do not need to be repeated if performed as part of the ARGX-113-2009 EoTP visit.

^b Day X applies when efgartigimod PH20 SC is initiated (refer to Section 6.3). Efgartigimod PH20 SC treatment will be started on day X, which can be the same day as the day the relapse is confirmed. Subsequent visits will be relative to day X, except for the EoTP visit that will take place 48 weeks after baseline for all participants.

- ^c Participants who stopped receiving efgartigimod PH20 SC after rollover but before protocol amendment 2 is effective will enter the observation period with visits every 8 weeks. Efgartigimod PH20 SC will be initiated at the investigator's discretion or if relapse occurs during the study. Participants who initiate efgartigimod PH20 SC must follow the SoA in [Table 2](#) as of day X (refer to [Section 6.3](#) for more details).
- ^d Visit F1 (EoTP + 4 weeks) is only applicable for participants receiving efgartigimod PH20 SC at week 48.

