5.5. Criteria for Temporarily Delaying Enrollment/IMP Administration

If IMP was temporarily interrupted at the time of the week 36/EoTP visit in ARGX-113-2009 (because of any reason as described in the ARGX-113-2009 protocol), participants can roll over to ARGX-113-2010 and have to follow the SoA per Table 1 until the investigator has determined that it is safe for the participant to receive treatment. If the participant requires treatment with efgartigimod PH20 SC, they must follow SoA per Table 2 as of day X.

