6.3.1. Participants Who Roll Over After Protocol Amendment 2 Is Effective

Situation 1: At roll over to this study

These participants will receive efgartigimod PH20 SC while maintaining the ARGX-113-2009 blinded treatment allocation of IMP (refer to Section 6.4).

- Participants in the placebo arm in ARGX-113-2009 will receive [REDACTED] of efgartigimod PH20 SC 1000 mg ([REDACTED] efgartigimod PH20 SC [REDACTED] on days 1 and 8, followed by once-weekly injections of efgartigimod PH20 SC 1000 mg.
- Participants in the efgartigimod PH20 SC arm in ARGX-113-2009 will receive [REDACTED] [REDACTED] followed by once-weekly injections of efgartigimod PH20 SC 1000 mg.

Situation 2: During this study's treatment period

Participants will continue receiving efgartigimod PH20 SC and may receive TCS or concurrent OCS according to the investigator's clinical judgment (refer to Section 6.9.1).

6.3.2. Participants Who Are Ongoing in This Study When Protocol Amendment 2 Is Effective

Situation 3: Participants not receiving efgartigimod PH20 SC when protocol amendment 2 is effective

3A: Participants who are not receiving any BP therapy (ie, these participants achieved CR or PR while off concurrent BP therapy for ≥ 8 weeks before protocol amendment 2 was effective)

- Once protocol amendment 2 is effective, efgartigimod PH20 SC may be initiated at the investigator's discretion. If the participant relapses and requires additional BP therapy, efgartigimod PH20 SC must be initiated (██████████) on days 1 and 8 followed by once-weekly injections of efgartigimod PH20 SC 1000 mg).

3B: Participants who are being treated with rescue therapy that started in ARGX-113-2009

- Rescue therapy will be tapered or discontinued (refer to Section 6.9.2) and efgartigimod PH20 SC will be initiated (██████████) on days 1 and 8 followed by once-weekly injections of efgartigimod PH20 SC 1000 mg).

Situation 4: Participants who are receiving efgartigimod PH20 SC when protocol amendment 2 is effective

4A: Participants who are receiving efgartigimod PH20 SC with or without concurrent OCS

- These participants will continue receiving efgartigimod PH20 SC and will continue their OCS tapering course.

4B: Participants who are receiving efgartigimod PH20 SC and who are receiving rescue therapy that started in ARGX-113-2009

- Rescue therapy will be tapered or discontinued (refer to Section 6.9.2) and efgartigimod PH20 SC treatment will be maintained.

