Treatment	Treatment period 2/ On IMP treatment	First IMP administration date/time in treatment period 2	
For participants with a subsequent Off IMP subperiod:
 
Last IMP administration date/time in treatment period 2.
 
For other participants:
 
Date of week 48 or EDV visit^c, with 23:59 added as time part.
 
For participants who don't have a week 48 or EDV visit: date of last contact, with 23:59 added as time part.

	Treatment period 2/ Off IMP treatment	Last IMP administration date/time in treatment period 2 + 1 minute	
Date of week 48 or EDV visit^c, with 23:59 added as time part.
 
For participants who don't have a week 48 or EDV visit: date of last contact, with 23:59 added as time part.

	Statistical Analysis Plan	
ARGX-113-2010	Final analysis	Final 1.0 of 29APR2025

Phase	Period/Subperiod	Start	End
Follow-up		End of previous phase + 1 minute	Date of last contact, with 23:59 added as time part.

- ^a First IMP administration is considered to occur on the ARGX-113-2010 baseline visit if the date of first IMP administration equals the scheduled baseline visit start date (SVSTDTC) or end date (SVENDTC), or if the first IMP administration occurs on an unscheduled baseline visit. In either case, the first phase starts with SVSTDTC of the first scheduled or unscheduled baseline visit.
- ^b A new treatment period is considered for participants with relapse after achieving CR or PR while being off concurrent BP therapy for ≥ 8 weeks before protocol amendment 2 was effective, or at the investigator's discretion after protocol amendment 2 was effective. For programming purposes, a new treatment period will be considered if a participant has a gap of at least 4 weeks (28 days) between two consecutive IMP administrations that cannot be attributed to missed visits or non-efficacy related reasons documented on the study drug administration eCRF form.
- ^c SVENDTC of the last scheduled or unscheduled week 48 or early discontinuation visit will be used.

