Else, the participant will be considered a non-responder for CROff without IMP. Participants who enter the ARGX-113-2010 study under protocol version 3 (26 April 2024) or 4 (02 May 2024) will be considered non-evaluable for this endpoint. Furthermore, participants who were randomized to the placebo arm in the ARGX-113-2009 study and who enter the ARGX-113-2010 study in the observation phase, will be considered non-evaluable for this endpoint in the observation phase.

- 6) Participants achieving CR or PR while off both OCS and efgartigimod PH20 SC for ≥ 8 weeks (CR/PROff without IMP). A participant will be considered a

	Statistical Analysis Plan	
ARGX-113-2010	Final analysis	Final 1.0 of 29APR2025

responder for CR/PROff without IMP if the following criteria are met simultaneously for ≥ 8 weeks (56 days):

- The participant's reported disease status is CR or PR (continuously or alternately)
- The participant is off OCS therapy
- The participant is off IMP
- The participant does not receive any rescue therapy (as indicated by the investigator on the eCRF)

Else, the participant will be considered a non-responder for CR/PROff without IMP. A participant will be considered non-evaluable for this endpoint using the same rules as for CROff without IMP.

- 7) Duration of sustained remission will be calculated for participants achieving CR while off both OCS and efgartigimod PH20 SC for ≥ 8 weeks (i.e., responders for CROff without IMP) within a treatment period.
 - Start date of sustained remission is 1 week (7 days) after the last IMP administration in the treatment period
 - End date of sustained remission is:
 - the start date of first relapse after achieving CROff without IMP
 - the start date of a (next) treatment period
 - the start date of OCS therapy after achieving CROff without IMP
 - the start date of a rescue therapy after achieving CROff without IMP
 whichever comes first. If none of the above occurs, the participant will be censored at the end date of the study (end date of last phase).
 - Duration of sustained remission (in days) = end date - start date + 1
- 8) Relapse will be evaluated for participants having or achieving CDA, CR or PR during the treatment period (or observation phase). The evaluation period for relapse is till the end of the treatment period (or observation phase) in case a (next) treatment period starts, or else till the end of the study. Only the first relapse in a treatment period (or observation phase) will be considered.

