- 9) Time to relapse:
 - Start date is the first day with status CDA, CR or PR in the treatment period (or observation phase)
 - End date is:
 - the start date of first relapse after having or achieving CDA, CR or PR
 - the end date of the study (end date of last phase), if no relapse
 - Time to relapse (in days) = end date - start date + 1
- 10) For participants with relapse, severity of (first) relapse will be calculated as the BPDAl total score at the onset of relapse (use the first available nonmissing BPDAl total score in the interval of relapse) minus the BPDAl total score at the preceding visit (use the most recent preceding visit for which a nonmissing BPDAl total score is available). Severity of relapse will be categorized as <0 , $0- <10$, $10- <20$, $20- <30$, or >30 .

	Statistical Analysis Plan	
ARGX-113-2010	Final analysis	Final 1.0 of 29APR2025

The following endpoints will be derived **overall**:

- 11) Changes and percent changes from study baseline will be calculated for BPDAI activity and total score.
- 12) Changes from study baseline will be calculated for itch NRS 24-hour average and worst scores.
- 13) C-GTI: Composite Glucocorticoid Toxicity Index comprises the Aggregate Improvement Score (AIS) and the Cumulative Worsening Score (CWS). Details of AIS and CWS derivations are specified in appendix 9.1.
- 14) A total ABQOL score is calculated as the sum of all 17 items score 0 to 3 with higher score indicating worse condition. Missing items are imputed with the average score of the present items if at least half (9) of the items are present. The total score is rounded to the highest integer.
- 15) Changes from study baseline will be calculated for EQ-5D-5L VAS score, DLQI score and total ABQOL score.

4.1.3 *Presentation of results*

Efficacy results will be presented for the ROL analysis set, unless mentioned otherwise. For tables by analysis visit, only the study baseline and last assessment analysis visits will be shown. Other analysis visits will be included in listings.

A frequency tabulation will be created for the number and percentage of participants who achieved CROff at least once during the study (i.e., in any treatment period). The table will also present the number of participants who are evaluable for the endpoint at least once during the study. This number will serve as denominator for the percentage calculation. This table will be based on the SAF analysis set.

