Similar frequency tabulations will be created for the number and percentage of participants who achieved:

- CR/PROff
- CRmin
- Treatment failure

Similar frequency tabulations, based on the ROL analysis set, will be created for:

- CROff without IMP
- CR/PROff without IMP
- Relapse

Duration of sustained remission and time to relapse will be descriptively presented with median times, quantiles and number and percentage of censored observations and observations with event. Only the participant's first evaluation during the study will be included as observation.

Duration of sustained remission will be presented for the SAF analysis set.

A frequency tabulation will be created for categorized severity of relapse, for the participant's first relapse during the study.

	Statistical Analysis Plan	
ARGX-113-2010	Final analysis	Final 1.0 of 29APR2025

Descriptive statistics will present the actual values, changes and percent changes from study baseline of the BPDAl activity and total scores per analysis visit (baseline and last assessment).

Frequency tabulations will be provided for the outcome of IGA-BP per analysis visit (baseline and last assessment). Additionally, cumulative percentages (starting with the best outcome result) will be calculated.

Descriptive statistics will present the actual values and changes from study baseline of the itch NRS 24-hour average and worst scores per analysis visit (baseline and last assessment).

Descriptive statistics will be provided for the C-GTI scores AIS and CWS at the last assessment.

Frequency tabulations will be provided for the outcomes of the ABQOL (17 items), EQ-5D-5L (5 dimensions) and DLQI (10 items), similar to the frequency tabulations of the IGA-BP outcomes. Descriptive statistics on absolute values and changes from study baseline for EQ-5D-5L VAS score, DLQI score and Total ABQOL score will be calculated per analysis visit (baseline and last assessment), similar to the descriptive statistics of the itch NRS scores.

Listings will be created for:

- Disease status, including the derived response variables (CROff, CR/PROff, CRmin, etc.)
- Duration of sustained remission and time to relapse, including the reason for censoring (if applicable) and the severity of relapse
- Lesion assessments
- BPDAl assessments
- IGA-BP assessments
- Itch NRS assessment
- Calculated C-GTI scores and complementary GTI specific list (GTI-SL)
- ABQOL, EQ-5D-5L and DLQI data

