14.2 EFFICACY DATA

EFFICACY (14.2.1.X)

14.2.1.1	CRoff: Proportion of Participants Who Achieved CRoff	SAF	EFT07b
14.2.1.2	CR/PROff: Proportion of Participants Who Achieved PR/CRoff	SAF	EFT07b
14.2.1.3	CRmin: Proportion of Participants Who Achieved CRmin	SAF	EFT07b
14.2.1.4	CRoff Without IMP: Proportion of Participants Who Achieved CRoff Without IMP	ROL	EFT07b
14.2.1.5	CR/PROff Without IMP: Proportion of Participants Who Achieved CR/PROff Without IMP	ROL	EFT07b
14.2.1.6	Sustained Remission: Kaplan-Meier Estimates of Duration of Sustained Remission	SAF	EFT09a
14.2.1.7	Relapse: Proportion of Participants with Relapse	ROL	EFT07b
14.2.1.8	Relapse: Kaplan-Meier Estimates of Time to Relapse	ROL	EFT09a
14.2.1.9	Relapse: Frequency Tabulation of Severity of Relapse	ROL	EFT07a
14.2.1.10	BPDAI: Descriptive Statistics of Actual Values, Changes From Baseline, and Percent Changes From Baseline in BPDAI Activity Score over Time	ROL	PDT01
14.2.1.11	BPDAI: Descriptive Statistics of Actual Values, Changes From Baseline, and Percent Changes From Baseline in BPDAI Total Score over Time	ROL	PDT01
14.2.1.12	IGA-BP: Frequency Tabulation of IGA-BP Score Over Time	ROL	EFT07d
14.2.1.13	Itch NRS: Descriptive Statistics of Actual Values and Changes From Baseline in Itch NRS 24-hour Average Score over Time	ROL	EFT03a
14.2.1.14	Itch NRS: Descriptive Statistics of Actual Values and Changes From Baseline in Itch NRS 24-hour Worst Score over Time	ROL	EFT03a
14.2.1.15	Treatment Failure: Proportion of Participants with Treatment Failure	ROL	EFT07b
14.2.1.16	C-GTI: Descriptive Statistics of CWS and AIS over Time	ROL	EFT03a
14.2.1.17	ABQOL: Frequency Tabulation of ABQOL 17 Items Over Time	ROL	EFT07d

	Statistical Analysis Plan	
ARGX-113-2010	Final analysis	Final 1.0 of 29APR2025

14.2.1.18	ABQOL: Descriptive Statistics of Actual Values and Changes From Baseline in ABQOL Total Score over Time	ROL	EFT03a
14.2.1.19	EQ-5D-5L: Frequency Tabulation of EQ-5D-5L 5 Dimensions Over Time	ROL	EFT07d
14.2.1.20	EQ-5D-5L: Descriptive Statistics of Actual Values and Changes From Baseline in EQ-5D-5L VAS Score over Time	ROL	EFT03a
14.2.1.21	DLQI: Frequency Tabulation of DLQI 10 Items Over Time	ROL	EFT07d
14.2.1.22	DLQI: Descriptive Statistics of Actual Values and Changes From Baseline in DLQI Score over Time	ROL	EFT03a
PHARMACODYNAMICS (14.2.3.X)			

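### Time to relapse runs to the end of the study for participants whose relapse window has already closed, so the Kaplan-Meier curve in Table 14.2.1.8 is too favourable

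*SAP*

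**What the plan says.** SAP section 4.1.2 derives items 5 to 10 separately for each treatment period and for the observation phase. Item 8 sets the window for relapse: "The evaluation period for relapse is till the end of the treatment period (or observation phase) in case a (next) treatment period starts". Otherwise the window runs to the end of the study. Only the first relapse in the period or phase is considered.

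Item 9 gives time to relapse two possible end dates: the start of the first relapse, or "the end date of the study (end date of last phase), if no relapse". The start of a next treatment period is not among them. Item 7, on duration of sustained remission, does list it.

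Section 4.1.3 restricts the time-to-event displays to one record per participant, the "first evaluation during the study will be included as observation". The display is Table 14.2.1.8, "Relapse: Kaplan-Meier Estimates of Time to Relapse", on the rollover set.

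The documents provide for a next treatment period that starts without a relapse:

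- Protocol section 6.3.2, Situation 3A, for participants off all BP therapy: "Once protocol amendment 2 is effective, efgartigimod PH20 SC may be initiated" at the investigator's discretion. SAP Table 2, footnote b, recognises a new treatment period at the investigator's "discretion after protocol amendment 2 was effective".
- Situation 3B in the same section: participants on rescue therapy and not on IMP start IMP.
- Protocol section 5.5: participants whose IMP was interrupted at rollover wait "until the investigator has determined that it is safe for the participant to receive treatment".

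**The concern.** Items 8 and 9 use different ends for the same record. Take a participant who has CDA, CR or PR and whose observation phase or treatment period 1 ends with a relapse-free start of IMP. Under item 8 the record can produce no event after that start. Under item 9 it counts as at risk and relapse-free until the end of follow-up. A later relapse belongs to a later evaluation, which section 4.1.3 keeps out of the table.

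The error has one direction: it makes time to relapse look longer. Protocol section 2 names relapse prevention as something the study will evaluate, and medians and quantiles are what the SAP reports for this endpoint. Moving the censoring date changes neither the number of events nor the number of censored records, so the counts in Table 14.2.1.8 would not reveal the problem. Tables 14.2.1.7 (proportion with relapse) and 14.2.1.9 (severity) look across the whole study and can include a relapse that Table 14.2.1.8 omits.

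**Working it through.** The plan states no relapse rate, event count or number of switches, so there is no figure of its own to reproduce. The check applies the dates first, then puts a range on the bias.

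**Dates.** Take a 56-week study with CDA, CR or PR from week 0 and a next treatment period at week 24. Item 8 gives 24 × 7 = 168 evaluable days. Item 9 gives 56 × 7 + 1 = 393 days. The difference, 225 days, is time in which no event can count. The same sum gives 337 days for a start at week 8, 281 at week 16 and 78 at week 45, the latest start that protocol section 6.3 allows.

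**Bias model.** These inputs are assumptions: 56-week relapse risk R of 30%, 50% or 70% with constant hazard; a share p of 5%, 20% or 40% assigned to switch at week s if still relapse-free; switching independent of relapse risk.

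- Hazard: h = −ln(1 − R)/56 per week.
- Censored at the switch: S(56) = 1 − R.
- As written: S(56) = (1 − p)·exp(−56h) + p·exp(−hs).
- Bias = p·[exp(−hs) − exp(−56h)].
- Share who actually switch relapse-free = p·exp(−hs).

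For s = 24:

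| R | h | exp(−24h) | Censored at switch | As written, p = 5% | p = 20% | p = 40% |
|---|---|---|---|---|---|---|
| 30% | 0.00637 | 0.858 | 0.700 | 0.708 | 0.732 | 0.763 |
| 50% | 0.01238 | 0.743 | 0.500 | 0.512 | 0.549 | 0.597 |
| 70% | 0.02150 | 0.597 | 0.300 | 0.315 | 0.359 | 0.419 |

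The bias in percentage points is 0.8 to 1.5 (p = 5%), 3.2 to 5.9 (20%) and 6.3 to 11.9 (40%). The shares actually switching relapse-free are 3.0% to 4.3%, 11.9% to 17.2% and 23.9% to 34.3%.

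Moving s widens the range. The largest value is 0.4 × (0.773 − 0.300) = 18.9 points (s = 12, R = 70%, p = 40%). The smallest is 0.05 × (0.795 − 0.700) = 0.5 points (s = 36, R = 30%, p = 5%).

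**Quantiles, s = 24.** After week 24 the curve as written is (1 − p)·exp(−ht) + p·exp(−24h). At R = 70% the median is ln 2/0.0215 = 32.2 weeks when censored at the switch. As written it is 32.7, 34.6 or 38.7 weeks for p = 5%, 20% or 40%. At R = 30% the time at which 25% have relapsed moves from 45.2 weeks to 46.4, 50.9 or not reached.

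**Simulation.** A Kaplan-Meier simulation of the same scenarios (200,000 participants each) agreed with the table to about 0.2 points. A second one (400,000 participants) spread the switch evenly over weeks 8 to 45 and assumed a 50% relapse risk at week 48. As written, the estimated week-48 risk was 48.1%, 46.2% and 42.4% for p = 10%, 20% and 40%. The median moved from 48.0 weeks to 51.0, 54.8 and not reached by week 56. Censoring at the switch returned the assumed risk to within 0.2 points.

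**The case against.** The strongest objection is that item 9 does not repeat item 8's period limit. Read alone, it could mean follow-up through the whole study with later relapses counted, and then no event-free time is credited. That reading conflicts with item 8, with derivation by period and with the first-evaluation rule, so item 9 needs correcting on either reading. Two programmers could otherwise produce two different curves.

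Second, the protocol defines no estimand, so bias depends on the target. The figures above take relapse-free time before any switch. If the target were relapse-free status regardless of re-treatment, the hazard after the switch would matter. With R = 50%, p = 20%, s = 24 and that hazard halved (an assumption), the inflation is 0.549 − (0.400 + 0.149 × 0.820) = 2.7 points instead of 4.9. The direction is the same.

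Third, the upper figures need a 40% switch share, which nothing in the documents supports. After amendment 2 all participants receive IMP at rollover, and Situations 3A and 3B cover only those already in the study and off IMP. The affected group is therefore mainly people who entered before the amendment. This stands.

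Fourth, the correction does not make Tables 14.2.1.7 and 14.2.1.9 agree with Table 14.2.1.8, because a relapse after the switch still enters only the first two. This also stands, although a listed censoring reason would explain the difference.

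Finally, the endpoint is secondary and descriptive and no test depends on it. That limits the consequence but does not make the estimate right.

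**Conclusion.** The concern holds. As written, item 9 keeps relapse-free switchers at risk after their item 8 window has closed, and this can only lengthen apparent time to relapse. How many participants are affected is not known from the documents. With few the effect is negligible. With 20% assigned a switch at week 24 it is 3.2 to 5.9 points at week 56, given a constant hazard, a 56-week relapse risk of 30% to 70% and switching unrelated to relapse risk. Over all the scenarios tried the range is 0.5 to 18.9 points, with the top end reached only under assumptions the documents do not support. It should be fixed before the analysis is run: the correction is small, and a reader of the table could not detect the error.

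**What to change.** In item 9, state that a participant without relapse is censored at the earlier of the start of the next treatment period and the end of the study.

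Add a same-day rule: a relapse with a start date on or before the day the next treatment period starts is an event of the preceding period or phase. Protocol Table 2, footnote b, says treatment starts on day X, "which can be the same day as the day the relapse is confirmed", and SAP section 2.2.1 sends untimed efficacy assessments on a switch day to the new phase or period. If that allocation were applied to the relapse date, the relapse that triggered treatment could be lost from the first evaluation. The rule should also say whether a switch-day BPDAI score may serve as the onset score in item 10.

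Show the start of the next treatment period as a censoring reason in Listing 16.2.6.2, and footnote Table 14.2.1.8 to say that discretionary starts may be informative censoring. Relapses and person-time by On IMP, Off IMP or follow-up, and observation phase could be added as supportive description. These states are not randomised and cannot show that maintenance treatment prevents relapse.

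The cost is two sentences of SAP text and one censoring-reason code. The period start dates already exist under SAP Table 2. The downside is more early-censored records, and censoring at a discretionary start may not be independent of relapse risk. The new censoring date alone leaves the event count unchanged; the same-day rule may change it.

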Escalated dosages of OCS are defined as prednisone (or equivalent OCS) 0.5 mg/kg/day for 1 to 3 weeks, followed by 0.75 mg/kg/day for ≤ 3 weeks, and 0.75 or 1.0 mg/kg/day for a final optional week.
- Transient lesions New lesions that heal within 1 week or pruritus lasting < 1 week
- Nontransient lesions New lesions that do not heal within 1 week or pruritus continuing > 1 week
- Minimal OCS therapy An oral prednisone (or equivalent OCS) dosage of ≤ 0.10 mg/kg/day
Note: For the purpose of this protocol, “oral prednisone” refers to doses/dosages of prednisone or an alternative, equivalent OCS (eg, prednisolone).
- Complete remission (CR) The absence of new lesions, complete healing of existing lesions, and absence of pruritus (except postinflammatory changes, including hypo/hyper pigmentation or skin damage)
- Partial remission (PR) The presence of only new transient lesions

- Sustained remission
 - For participants ongoing in the study when protocol amendment 2 is effective:
 - Healing of lesions with no nontransient lesions (ie, BPDAI activity score of 0) and absence of pruritus while the participant has been off both concurrent BP therapy and off efgartigimod PH20 SC for ≥ 8 weeks
 - New lesions that heal within 1 week or pruritus lasting < 1 week and clearing without treatment will not be considered to change the condition of sustained remission.
 - For participants rolling over after protocol amendment 2 is effective:
 - Healing of lesions with no nontransient lesions (ie, BPDAI activity score of 0) and absence of pruritus while the participant has been off concurrent BP therapy for ≥ 8 weeks.
 - New lesions that heal within 1 week or pruritus lasting < 1 week and clearing without treatment will not be considered to change the condition of sustained remission.
- Relapse
 - Appearance of 3 or more new lesions/month (blisters, eczematous lesions, or urticarial plaques) or at least 1 large (> 10 cm diameter) eczematous lesion or urticarial plaque that does not heal within 1 week, or extension of established lesions or daily pruritus in a participant who has achieved CDA.

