3. OBJECTIVES, ENDPOINTS, AND ESTIMANDS

Table 4: Study ARGX-113-2010 Objectives and Endpoints

Objectives	Endpoints
Primary	
To assess the long-term safety and tolerability of treatment with efgartigimod PH20 SC in participants with BP	
 • Incidence and severity of treatment-emergent AEs, SAEs, and AESIs • Rate of treatment discontinuation because of safety concerns
Secondary	
To assess the long-term efficacy and durability of response with efgartigimod PH20 SC treatment in participants with BP	
 • Proportions of participants achieving^a: 
 – CR while off OCS for ≥ 8 weeks – CR or PR while off OCS for ≥ 8 weeks – CR while on minimal OCS therapy for ≥ 8 weeks. (Minimal OCS therapy is defined as ≤ 0.10 mg/kg/day of prednisone [or an equivalent dose of another OCS]) – CR while off both OCS and efgartigimod PH20 SC for ≥ 8 weeks^b – CR or PR while off both OCS and efgartigimod PH20 SC for ≥ 8 weeks^b • Duration of sustained remission • Proportion of participants who relapse • Time to relapse • Incidence and severity of relapse • BPDAI activity scores, IGA-BP scores, and itch NRS over time • Rate of treatment failure
Additional secondary	
To evaluate the impact of efgartigimod PH20 SC treatment in reducing long-term glucocorticoid-associated toxicity in participants with BP	GTI-related scores, including the GTI-AIS, GTI-CWS, and GTI-SL over time
To evaluate the impact of efgartigimod PH20 SC treatment on QoL in participants with BP	EQ-5D-5L, DLQI, and ABQoL scores over time
To evaluate the PD and immunogenicity of efgartigimod PH20 SC in participants with BP	
 • Percent change from baseline over time for anti-BP180 and anti-BP230 antibody levels • Incidence and prevalence of ADA against efgartigimod (serum levels)

Objectives	Endpoints
Exploratory	
████████████████████ ████████████████████	██ ████████

^a These endpoint criteria can only be met when participants are off rescue therapy.

^b The endpoint applies only to participants who have stopped receiving efgartigimod PH20 SC before protocol amendment 2 is effective.

No estimands have been defined for this OLE study.

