8.2.1.3. Bullous Pemphigoid Disease Area Index

BP disease activity will be assessed by the investigator using the BPDAI.³ The BPDAI is an internationally validated tool to objectively measure disease activity. The BPDAI differentiates scores for skin (erosions/blisters and urticaria/erythema) and mucous membrane activity in several anatomical locations. In addition, separate scores for damage (eg, pigmentation) are recorded to account for healing lesions.^{1,3}

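### The relapse severity categories leave out a change of exactly 30, and severity rests on an undefined BPDAI total score where the protocol's related definitions rest on disease activity

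*SAP*

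**What the plan says.** The protocol (section 3, Table 4) lists "Incidence and severity of relapse" among its secondary endpoints and names no score for it. The SAP supplies the rule in 4.1.2 item 10. Severity is the BPDAI "total score at the onset of relapse", taken as the first nonmissing value in the relapse interval, minus the total score at the most recent earlier visit that has one. The sentence that begins "Severity of relapse will be categorized as" then lists five bins: <0, 0-<10, 10-<20, 20-<30 and >30.

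SAP 4.1.3 puts the bins to use: "A frequency tabulation will be created for categorized severity of relapse", limited to each participant's first relapse in the study. The output is Table 14.2.1.9. Individual values go to Listing 16.2.6.2.

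On the scores themselves:

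- SAP 4.1.2 item 11 treats activity and total as two variables: "Changes and percent changes from study baseline will be calculated for BPDAI activity and total score". The SAP does not say how the total is formed.
- Protocol 8.2.1.3 describes skin and mucous membrane activity scores and adds that "separate scores for damage (eg, pigmentation) are recorded to account for healing lesions". It does not mention a total.
- The protocol's BPDAI endpoint is the activity score: "BPDAI activity scores, IGA-BP scores, and itch NRS over time".
- The protocol's Definitions of Terms tie sustained remission to a "BPDAI activity score of 0".

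**The concern.** There are two separate problems in one derivation rule.

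The first is a gap. A participant whose score rises by exactly 30 at relapse has a valid severity value but no row in the table. The programmer would have to improvise, or the percentages would not add up.

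The second is the choice of score. A relapse in this protocol is an event of active disease, and residual pigmentation or skin damage plays no part in it. A severity measure for that event would be expected to track activity. Item 10 uses the total without giving a reason and without defining it. If the total takes in damage, then fading or accumulating skin damage since the preceding visit is added to the change caused by the relapse, and the reported band reflects both. Severity of relapse is a named secondary endpoint in a study that also asks whether long-term treatment can prevent relapse (protocol section 2), so the table should measure what its title says.

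**Working it through.** **Category check.** Inputs: the five bins of SAP 4.1.2 item 10, coded as printed, with x the change in score. Each value from -100 to +200 in steps of 0.5 was assigned to every bin whose condition it met.

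| x | Bins as printed | Bins with the top one written as >=30 |
|---|---|---|
| 29 | 20-<30 | 20-<30 |
| 29.5 | 20-<30 | 20-<30 |
| 30 | none | >=30 |
| 30.5 | >30 | >=30 |
| 31 | >30 | >=30 |

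As printed, 30 is the only uncovered value and no value falls in two bins. With >=30, every value falls in exactly one bin. A sign lost in text extraction is unlikely, because inclusive signs survive elsewhere in the same document, for example in the age and BMI categories of SAP 3.2.2.

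SAP 2.4.1 sets the denominator of frequency tables as participants with nonmissing values. A change of 30 is nonmissing, so on that rule the participant stays in the denominator without a row, and the percentages sum to less than 100. Item 10 does not address the case.

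**Which score the other definitions use.**

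| Place | Basis |
|---|---|
| Protocol, Definitions of Terms, relapse | New lesions, a large lesion that persists, spread of existing lesions, or daily itch |
| Protocol, Definitions of Terms, complete remission | Postinflammatory pigment change and skin damage are disregarded |
| Protocol, Definitions of Terms, sustained remission | Activity score of 0 and no itch |
| Protocol section 3, BPDAI endpoint | Activity score |
| SAP 3.2.2, baseline BPDAI bands | Activity score (<20, 20-56, >56) |
| SAP 4.1.2 item 10, relapse severity | Total score |

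In this comparison item 10 is the only entry that rests on the total.

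**What the total contains.** Item 11 shows that the total differs from activity. Protocol 8.2.1.3 describes only one other kind of score, damage. The natural inference is total = activity + damage, but it is not stated anywhere.

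**Effect on the bands, if total = activity + damage.** All values below are invented to show the arithmetic; none comes from the documents.

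| Change in activity | Change in damage | Change in total | Band by activity | Band by total |
|---|---|---|---|---|
| +12 | -4 | 12 - 4 = +8 | 10-<20 | 0-<10 |
| +8 | +3 | 8 + 3 = +11 | 0-<10 | 10-<20 |
| +5 | -6 | 5 - 6 = -1 | 0-<10 | <0 |
| +33 | -3 | 33 - 3 = +30 | >30 | none |

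The shift can go either way. The documents give no figure for the change in damage between adjacent visits, so the frequency of such shifts cannot be calculated.

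**The case against.** The strongest reply is that only the gap at 30 is established. Neither document defines the total, so the inclusion of damage is an inference that needs the instrument's scoring rules to confirm. That is correct, and everything said here about band shifts is conditional on it. It does not remove the point: if the inference is wrong, a secondary endpoint still rests on a score that the plan does not define.

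Four stronger readings are tempting, and the documents do not support them.

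- *The SAP contradicts the protocol.* It does not. The protocol names no score for relapse severity, and the activity-score endpoint is a separate item. The SAP was free to choose; it made an unexplained choice.
- *The <0 category shows that damage distorts the measure.* It shows nothing of the kind. Relapse can be declared on daily itch alone, which protocol 8.2.1.4 measures on a separate scale, and the score used is the first one available in the relapse interval, which may postdate onset. An activity change can therefore be negative too, and an activity-based rule would still need that category.
- *Relapses will be placed in the wrong band.* This assumes both the composition of the total and a material change in damage since the preceding visit. On the planned schedule that visit is about 4 weeks earlier on treatment after week 8, or 8 weeks earlier off treatment, and the interval is longer if scores are missing. The size of any damage change over that time is unknown.
- *A participant at exactly 30 is lost from the analysis.* The value remains in the listing and, under SAP 2.4.1, in the denominator. What is missing is a row.

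It also stands that the study tests no hypothesis and that the BPDAI activity score is summarized separately in Table 14.2.1.10.

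**Conclusion.** The concern holds in two parts of different strength.

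The category gap is certain and needs no assumption: the rule fails as written at one value, 30.

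The score choice is a sound criticism, but it is not an error against the protocol. The total score is undefined, its use is not justified, and it departs from the activity basis of the protocol's related definitions. That it includes damage is a reasonable inference. Any shift between bands depends on that inference and on unknown changes in damage between visits.

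The reach is small: descriptive Table 14.2.1.9 and Listing 16.2.6.2, with no test and no effect on the primary safety endpoints. The change is still worth making, because severity of relapse is a named secondary endpoint and the correction is cheap.

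**What to change.** In SAP 4.1.2:

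1. Write the last severity category as >=30.
2. Define severity of relapse as the BPDAI activity score at onset minus the activity score at the preceding visit, keeping item 10's rules for choosing the two values. Keep the <0 category.
3. Present the total-score version as supportive.
4. State how the BPDAI total score is formed. If the total is kept as the main measure, give the reason.

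Both scores are already collected (SAP 4.1.1), so no new data are needed. The cost is a few lines of SAP text, one more derived variable, a supportive panel in Table 14.2.1.9 and a column in Listing 16.2.6.2. As the SAP is marked final, the change should be recorded in SAP section 6.
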